4.2 Justification for treatment regimen

Three hours of use for each device to allow for sufficient time for subjects to become familiar with the functional differences in each device to provide meaningful feedback on their experiences.

4.2.1 Screening and Enrollment Phase

Part 1: Subjects who are recruited from the general population will be screened for eligibility by answering questions about their general health and foot or ankle injuries. Subject demographics will be collected; however no medical record review will be conducted. Written informed consent will be obtained from eligible subjects.

Part 2: Subjects who are admitted for inpatient care following admission to Penn Presbyterian Medical Center will be identified and screened for eligibility. Written informed consent will be obtained from eligible subjects by Pennsylvania licensed medical professional. Video consent may be used.

4.2.2 Study Intervention Phase

Part 1: Enrolled healthy subjects will have the OsciPulse device applied by study or medical personnel according to the OsciPulse Instructions for Use. The subject will wear the device for a maximum of 3 hours while laying down. At the end of the study period the subject will receive an ultrasound scan of the deep venous system of the thigh/groin region to measure hemodynamics at a venous valve during immobility and during use of the OsciPulse device. Finally, the subject will participate in a questionnaire evaluation of their comfort and experience with the OsciPulse device. Participants will be compensated at \$50/ hour for their participation.

Part 2: After informed consent is obtained, baseline demographic and clinical data will be collected. The subjects will be randomized with equal allocation to either of the two treatment sequence groups:

- Group A (OsciPulse device then standard IPC device)
- Group B (standard IPC device then OsciPulse device)

For group A, the OsciPulse device will be applied to the subject on both legs in the first 3 hours. The subject will wear the device for the maximum number of hours as possible up to 3 hours. The [REDACTED] research team inquire with the subject if the device was removed during the testing period.. During the 3-hour period the study team will monitor for adverse events and a hemodynamic ultrasonography may be performed (when feasible) following the Ultrasound SOP. After 3 hours, the subject will complete the questionnaire evaluating the tolerability and safety of the device. In the following 3 hours, the standard IPC will be applied. Subjects will undergo the same procedure for compliance monitoring, adverse event monitoring, hemodynamic ultrasonography (when feasible), and questionnaire evaluation.

For group B, the same procedure will be performed but with the standard IPC in the first 3 hours and the OsciPulse device in the next 3 hours.

Participants will be compensated \$100 for their participation.

4.3 End of Study Definition

A participant is considered to have completed the study if he or she has completed the intervention phase of the study.

4.4 Allocation to Interventional Group

All enrolled subjects will be assigned to both interventions. [REDACTED] will allocate the treatment sequence groups (group A: OsciPulse then IPC and group B: IPC then OsciPulse) in a 1:1 ratio by using block randomization. Prior to the study launch, [REDACTED] will create 4 envelopes. Each envelope will contain a GreenPhire card that will contain subject compensation, and a randomization form for either group A or for group B. This group of 4 envelopes will maintain the 1:1 ratio of randomization to group A or group B. Once all 4 envelopes have been sealed, they will be shuffled so that none of the research team knows which envelope contains each randomization form. Once the envelopes have been shuffled, the [REDACTED] study team member will place them in a random order and write subject study ID number on the outside of the envelope, indicating which subject they will be used for. For the first group, this will generate randomization for subjects one through four. When a subject is enrolled, the subject will be assigned a study identification number and the CRC will select the envelope with corresponding study-ID number—this will serve as the patient randomization. This process will be repeated 4 additional times in order to provide randomization for subjects 5 – 20. Once the envelope has been selected, the study team member will open the envelope, deliver the GreenPhire card to the subject and record the subject's intervention group onto a spreadsheet. The randomization sequence spreadsheet, randomization assignment sheet, and envelope will be kept and maintained a [REDACTED], which will be secure and accessible only by [REDACTED] staff and the nursing staff.

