5.2 Exclusion Criteria

Part 1:

1. Injury to the lower limbs
2. Skin breaks, abrasion, or irritation in the area of the limb in contact with the OsciPulse device

Part 2:

1. Inability or contraindication to applying IPC to both legs
 - o Evidence of bone fracture in lower extremities
 - o Burns in the lower extremities, lacerations, ulcers, active skin infection or dermatitis, & ischemic limb in the legs at the site of IPC placement
 - o Acute ischemia in the lower extremities
 - o Severe peripheral vascular disease
 - o Amputated foot or leg on one or two sides
 - o Compartment syndrome
 - o Severe lower extremity edema
2. Subjects anticipated to require surgical intervention within six (6) hours of admission
3. Subjects with history of VTE (DVT or PE)

4. Previous vascular surgery
5. Pregnancy or within 6 weeks of postpartum period
6. Limitation of life support, life expectancy < 7 days or palliative care
7. Admitted to an outside hospital more than 24 hours prior to screening
8. A head-unit is unavailable for the 6 hours or more
9. At the discretion of the attending physician and / or clinical team, the subject's participation in the study is believed not to be in the best interest of the subject.

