6.6 Blinding

The intervention will not be blinded in this study

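### Fixed blocks of four with readable boundaries make about a third of the sequence assignments in Part 2 deducible in advance; varied, undisclosed block sizes would cheaply reduce this

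*Combined protocol and SAP*

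**What the plan says.** Section 4.4 describes block randomization by sealed envelope. Before launch, a team whose name is redacted "will create 4 envelopes", and "This group of 4 envelopes will maintain the 1:1 ratio of randomization to group A or group B", so each set holds two forms for OsciPulse first (A) and two for IPC first (B). After sealing, "they will be shuffled so that none of the research team knows which envelope contains each randomization form". Study IDs are then written on the outside: "For the first group, this will generate randomization for subjects one through four". For subjects 5 to 20, "This process will be repeated 4 additional times".

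At enrollment the CRC picks the envelope that carries the subject's ID. Then "the study team member will open the envelope, deliver the GreenPhire card to the subject and record the subject's intervention group onto a spreadsheet". The same section opens these records to a redacted staff group and to the nursing staff.

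Section 6.6 states: "The intervention will not be blinded in this study". Section 4.1 describes a single site. Section 4.4 describes no variation in block size, no central allocation, and no barrier between past assignments and the staff who recruit.

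**The concern.** Sealing and shuffling hide the order within a set of four only until the set begins to be used. Because each set is balanced, every opened envelope narrows what is left. In an open trial with a running log and visible block boundaries, a staff member who has followed the current block may know the next sequence before the next patient is approached.

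Entry leaves some room for judgement. Section 5.1 (Part 2, item 3) rests on the clinical team's view of expected mobility. Section 5.2 (Part 2, item 9) lets the clinical team decline when "the subject's participation in the study is believed not to be in the best interest of the subject". Under section 11.4.1 a CRC, the role that selects the envelope, may also witness video consent.

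Only the order is randomized, so two routes to bias are at stake:

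- **Period trends.** The paired t-test in sections 9.2.1 and 9.2.4 has no period or sequence term. Random order is what keeps a patient's change over the six hours out of the device difference.
- **Early leavers.** A subject who leaves during the first three hours has worn one device only. Section 9.2.2 counts adverse events under each device, and section 9.3 drops non-completers. Order therefore decides which device such a subject contributes to, and who is left in each sequence.

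**Working it through.** **Inputs (section 4.4).** Block size 4, two A and two B per block, first block subjects 1 to 4, process repeated four more times. Sample size: up to 20 enrolled (9.2.3); 15 to 20 evaluable (5.5).

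**The plan's own figure.** 4 × (1 + 4) = 20 envelopes, which matches subjects 1 to 20.

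**Certain assignments.** An assignment is certain when only one type of form remains in the block. A block of two A and two B has 6 equally likely orders.

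| Position in block | Chance it is certain | Chance the best guess is right |
|---|---|---|
| 1 | 0 | 1/2 |
| 2 | 0 | 2/3 |
| 3 | 1/3 (first two match: 2 of 6 orders) | 1/3 × 1 + 2/3 × 1/2 = 2/3 |
| 4 | 1 | 1 |
| Sum per block | 4/3 | 2.83 |

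- Share certain: (4/3)/4 = 33.3%.
- 20 subjects: 5 × 4/3 = 6.67 expected. The count is 5 + Binomial(5, 1/3), so at least 5 and at most 10.
- 15 subjects: 3 × 4/3 + 1/3 = 4.33 expected, or 28.9%.
- Best guess (the form with more copies left): 2.83/4 = 70.8% right, against 50% under full concealment.

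**How order enters the device difference.** Let a subject's VAS drift by d from the first period to the second. The OsciPulse-minus-IPC difference then contains −d in group A and +d in group B. With balanced random order these cancel in expectation. They fail to cancel if patients with different d are placed in different sequences. If nobody steers, d is unrelated to sequence and the bias is zero.

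**Alternatives.**

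- Fixed, known blocks of 2m have a certain share of 1/(m + 1): 25% for blocks of 6, 20% for blocks of 8, and 9.1% for one block of 20.
- Blocks of 4 or 6 chosen at random with equal chance, where staff know the two possible sizes but not the boundaries: a simulation of 20 subjects gives about 6% certain, or 0.06 × 20 = 1.2 subjects.
- Best-guess accuracy falls much less. Even fixed blocks of 6 leave it at 68.3%. The gain from varying sizes is the removal of certainty, not of all predictability.

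**Sequence split if recruitment stops at 15 enrolled.**

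- Fixed blocks of 4: always 8/7.
- Random 4/6 blocks: 9/6 at worst. This needs a block boundary at 12 (4+4+4 or 6+6: 1/8 + 1/4 = 3/8), then a block of 6 (1/2) whose first three forms match (2/20). That gives 3/8 × 1/2 × 1/10 = 1.9%.
- One shuffle of 20 (10 A, 10 B): 8/7 with probability 70%, 9/6 with 27%, 10/5 with 3%.

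**The case against.** The strongest reply is that this hardly matters in a crossover. Every subject is assigned both devices and the analysis is within subject, so foreknowledge cannot put different kinds of patient on different devices. The documents show no motive to steer. That stands, and it is why the priority is low. It does not remove the two routes through order, because the t-test has no period term and some subjects may leave after one device.

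A reader might infer more than the documents support in four ways.

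- **That the concealment sentence is simply false.** It describes the moment of shuffling and is true then. About two thirds of assignments also stay uncertain. Concealment is weakened, not absent.
- **That recruiters know the assignment before consent.** Redactions hide who allocates, who holds the spreadsheet and which staff group can see it. The nursing staff have access, but nothing shows that those who take consent or apply the discretionary exclusion consult it.
- **That the six losses allowed for in section 9.2.3 would fall unevenly as adverse events, for example 2 v 4.** Those six are losses of evaluability and include discharge, so they are not a count of adverse events. An uneven split also needs all six in the first period and staff who foresee them. Section 5.2 already excludes some foreseeable cases (surgery anticipated within six hours of admission, life expectancy under 7 days). Section 10.2.2 has relatedness judged clinically for each event.
- **That the VAS difference is biased by a known amount.** If a third of slots were steered and patients steered to one order differed in drift by g from those steered to the other, the shift would be g × (1/3)/2. With g of 10 to 20 mm that is 1.7 to 3.3 mm. No such g appears in the documents, and every certain slot would have to be steered.

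**Conclusion.** The point holds as a limited weakness in section 4.4. On average a third of assignments (6.7 of 20, or 4.3 of 15) are certain in advance for anyone who knows the earlier ones in the block. This assumes that IDs are issued in order; whether recruiting staff have that knowledge cannot be confirmed from the redacted text.

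The effect on results runs only through which patients get which order. It is zero without steering, and otherwise cannot be sized from the documents. They do not support a conclusion that the trial lacks concealment or that its device comparison is biased. Minor priority; label: cheap improvement.

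**What to change.** In section 4.4:

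- Keep the sealed envelopes, but draw block sizes at random, for example 4 and 6.
- Prepare and number all envelopes before the first Part 2 subject.
- Keep the order of block sizes out of the protocol and away from staff who screen and consent.
- Prepare enough envelopes to cover replacements. Section 5.5 allows enrollment beyond 20, and the present scheme stops at subject 20.
- Restate the concealment sentence so that it covers the whole of recruitment and not only the moment of shuffling.

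The cost is one rewritten paragraph, slightly more preparation, and a possible small sequence imbalance if recruitment stops mid-block (with 4/6 blocks, 9/6 at worst at 15 enrolled, in about 2% of cases).

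A single shuffle of all 20 envelopes should not be the lead fix. It lowers the certain share to 9%, but stopping at 15 gives 9/6 or worse about 30% of the time. Because the t-test has no period term, a shared period effect then enters the device difference multiplied by imbalance/N: 3/15 = 0.20 at 9/6 and 5/15 = 0.33 at 10/5, against 1/15 = 0.07 at 8/7. It also does not extend to replacements.

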4.5 Protocol-defined Enrollment Hold

Part 2: In the event a disproportionate number of subjects are enrolled with a singular diagnosis, the Investigator in consultation with the Sponsor may pause the study to enrollment to reevaluate or revise, or both, the enrollment strategy, the intended subject population, the statistical analysis, or several of these activities.

4.6 Study Endpoints

4.6.1 Primary Study Endpoints

The primary endpoint will be subject safety and tolerability. Safety will be evaluated by the presence of adverse events (See section 10) during the intervention. Tolerability will be evaluated by a subject reported questionnaire. Tolerability will be measured by the 100-mm visual analog scale (VAS) and through open ended question answers. The average distance on the VAS in each domain of the questionnaire will be compared between the OsciPulse device and standard IPC.

4.6.2 Secondary Study Endpoints

- Percentage of time wearing the OsciPulse and standard IPC devices
- Ultrasonographic hemodynamic parameters (Change in venous centerline velocity in the femoral vein and volume of venous valve sinus reversing flow at the sapheno-femoral junction or other valve site imaged)

5 STUDY POPULATION AND DURATION OF PARTICIPATION

5.1 Inclusion Criteria

Part 1:

1. Adult age ≥ 40 years old
2. Generally healthy without a current foot or ankle injury
3. No history of diagnosed vascular disease including: DVT, PE, VTE, peripheral vascular disease, post-phlebitic syndrome, or chronic venous insufficiency.
4. Mentally alert and understand English proficiently.
5. Able to give informed consent.

Part 2:

1. Adult age ≥ 18 years old
2. Admitted to Penn Presbyterian Medical Center.
3. Anticipated decreased level of mobility for at least 6 hours as determined by the clinical team in collaboration with [REDACTED].
4. Mentally alert and understand English proficiently.
5. Able to give informed consent.

5.2 Exclusion Criteria

Part 1:

1. Injury to the lower limbs
2. Skin breaks, abrasion, or irritation in the area of the limb in contact with the OsciPulse device

Part 2:

1. Inability or contraindication to applying IPC to both legs
 - o Evidence of bone fracture in lower extremities
 - o Burns in the lower extremities, lacerations, ulcers, active skin infection or dermatitis, & ischemic limb in the legs at the site of IPC placement
 - o Acute ischemia in the lower extremities
 - o Severe peripheral vascular disease
 - o Amputated foot or leg on one or two sides
 - o Compartment syndrome
 - o Severe lower extremity edema
2. Subjects anticipated to require surgical intervention within six (6) hours of admission
3. Subjects with history of VTE (DVT or PE)

4. Previous vascular surgery
5. Pregnancy or within 6 weeks of postpartum period
6. Limitation of life support, life expectancy < 7 days or palliative care
7. Admitted to an outside hospital more than 24 hours prior to screening
8. A head-unit is unavailable for the 6 hours or more
9. At the discretion of the attending physician and / or clinical team, the subject's participation in the study is believed not to be in the best interest of the subject.

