1.2 Schema

Figure 1. Study Schema

PART 1:

Visit 1

Total Subjects 3: Consent eligible participants

Visit 1

OsciPulse application and study procedure (3 hours)

Proceed from Part 1 to Part 2 if all subjects indicate a lack of “significant discomfort” during Part 1

PART 2:

Visit 1

Total Subjects up to 20: Screen, consent, and randomize eligible participants (within 24 hours from hospital admission)

Visit 2

Intervention 1 and study procedures (0-3 hours)

Visit 3

Intervention 2 and study procedures (3-6 hours)

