5.3 Subject Recruitment

Part 1: Subjects will be recruited with IRB approved recruitment materials

Part 2: Subjects admitted to Penn Presbyterian Medical Center will be screened by [REDACTED] for eligibility within the first 24 hours of admission.

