5.4 Duration of Study Participation

Part 1: The duration of study participation will continue for a maximum of 3 hours.

Part 2: The duration of study participation will continue for 6 consecutive hours.

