9 STATISTICAL PLAN

9.1 Part 1

Part 1 of the trial is designed to test the tolerability of the OsciPulse system on healthy subjects for 3 hours prior to the 6-hour trial on patients. This is to determine if there are any immediate comfort issues that can be addressed prior to use in the clinical setting. Healthy volunteers are not the target population for the OsciPulse device and will have different tolerability for discomfort than hospital patients, but we feel that this test will be a qualitative analysis of the product prior to use in the target population. Subjects will indicate if the device caused 1) no discomfort, 2) mild discomfort, or 3) significant discomfort. **We will require that all three subjects indicate that there was not “significant discomfort” as reported on the subject questionnaire before continuing to Part 2.** This will be confirmed by the monitor prior to continuation to Part 2.

9.2 Part 2

Part 2 of the trial is designed to assess the tolerability and hemodynamic efficacy of the OsciPulse device in the clinical setting. The Primary endpoint is tolerability, which will be evaluated with questionnaires scored with a visual analog scale and will be directly compared between the OsciPulse device and a reference therapy device. Evaluable subjects will have completed the 6-hour study time that includes 3 hours with both therapies. This allows for the comparison between the therapies that makes the data quantitative rather than subjective. We will further measure hemodynamic efficacy through vascular ultrasound measurements of venous flow

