9.2.3 Sample Size and Power Determination

This study is a Phase 2 trial aimed at determining the tolerability and safety of an external device so we will use a convenience sample size of up to 20 enrolled subjects. This was determined in part by allowing that within our targeted population up to 6 subjects could experience an event during the 6-hour study window (discharge, unexpected surgery, loss of consciousness, death), and we would still have 14 subjects with evaluable tolerability and safety data.

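### The Part 2 surgery exclusion runs for six hours from admission, but entry is allowed up to 24 hours after admission, so surgery foreseen during the study period need not be excluded (minor).

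*Combined protocol and SAP*

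**What the plan says.** Five parts of the Part 2 plan bear on this point.

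- **Surgery criterion.** Section 5.2, Part 2 exclusion 2, removes "Subjects anticipated to require surgical intervention within six (6) hours of admission". The clock starts at admission.
- **Entry window.** Section 5.3 has subjects screened "for eligibility within the first 24 hours of admission". The schema in Section 1.2 gives the same limit for all entry steps: "Screen, consent, and randomize eligible participants (within 24 hours from hospital admission".
- **Length of participation.** Section 5.4: "The duration of study participation will continue for 6 consecutive hours".
- **What counts as evaluable.** Section 9.2: "Evaluable subjects will have completed the 6-hour study time that includes 3 hours with both therapies". Section 9.3 leaves subjects who do not complete the protocol requirements out of the analysis.
- **Allowance for losses.** Section 9.2.3 allows for up to 6 of 20 subjects having an event in the six-hour study window, with these examples: "discharge, unexpected surgery, loss of consciousness, death". It concludes that "we would still have 14 subjects with evaluable tolerability and safety data".

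**The concern.** The six hours in exclusion 2 equal the six hours of participation, but the two periods start at different times. One starts at admission. The other starts when the subject enters, which can be up to a day later. For late entrants the exclusion period is over before the study period begins, so the criterion says nothing about an operation still to come.

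This matters because each subject serves as his or her own control. An operation in either three-hour period costs the whole paired comparison for that subject. The subject has by then been consented, randomized and possibly exposed to a device, with nothing to analyze. The loss allowance in Section 9.2.3 names only unexpected surgery, so foreseen surgery is not among the causes it was built on.

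**Working it through.** **The plan's own figure.** Section 9.2.3: 20 enrolled − 6 events = 14 evaluable. This reproduces. (Section 5.5 sets a minimum of 15 evaluable subjects. That difference is a separate matter and is not used here.)

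**Inputs.**
- Exclusion period: hours 0 to 6 after admission (Section 5.2).
- Permitted entry: hour t after admission, with t from 0 to 24 (Sections 1.2 and 5.3).
- Study period: hours t to t + 6 (Section 5.4), taking participation to start at entry. If the first device is applied some time after randomization, t is the later time and coverage is lower.

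**Formula.** Study hours covered by the exclusion = overlap of [0, 6] with [t, t + 6] = max(0, 6 − t).

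| Entry hour t | Study period (hours after admission) | Study hours covered | Share of 6 hours |
|---|---|---|---|
| 0 | 0–6 | 6 | 100% |
| 1 | 1–7 | 5 | 83.3% |
| 3 | 3–9 | 3 | 50% |
| 5 | 5–11 | 1 | 16.7% |
| 6 | 6–12 | 0 | 0% |
| 12 | 12–18 | 0 | 0% |
| 24 | 24–30 | 0 | 0% |

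Coverage is complete only for entry at the moment of admission. Entry from hour 6 to hour 24 has none: (24 − 6)/24 = 18/24 = 75% of the permitted entry hours.

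**Range under an assumption.** The documents do not say when subjects enter. Suppose entry is uniform from 0 to E hours, with E at least 6. The mean number of hours covered is the integral of (6 − t) from 0 to 6, divided by E, which is 18/E. As a share of six hours this is 3/E:
- E = 6: 3/6 = 50%
- E = 12: 3/12 = 25%
- E = 24: 3/24 = 12.5%

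**Worked case.** A subject is randomized at hour 12 with surgery planned for hour 15. Exclusion 2 covers hours 0 to 6 only, so it does not apply. The study period is hours 12 to 18. Surgery falls 15 − 12 = 3 hours in, at the change of device, so three hours on the second device cannot be completed as Section 9.2 requires. If surgery were planned for hour 13, the first period would be cut short as well.

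**Other criteria.** No other Part 2 criterion names surgery during the study period. Inclusion 3 asks for reduced mobility for at least six hours, which a patient awaiting surgery can satisfy. Exclusion 4 concerns past vascular surgery. Exclusion 9 is a best-interest judgment left to the attending physician or clinical team.

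**The case against.** The strongest reply is that the plan already absorbs the harm. Section 5.5 ends recruitment on evaluable subjects (15 to 20), lets the sponsor replace a subject who starts but is not evaluable, and lets the sponsor pause and revisit eligibility if too many fail. This largely stands. A reader might infer that each such subject removes 1 of 20, or 5%, of the analysis set, and the documents do not support that. Replacement is a reserved right, though, not a duty, and Section 4.4 describes randomization envelopes only for subjects 1 to 20.

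Second, there are practical filters. The clinical team takes part in the inclusion 3 judgment, the medical record is reviewed at pre-screening (Section 7.1), and exclusion 9 gives the team a veto. People who know the operating schedule are therefore likely to be consulted. This makes an obvious case less likely but does not close the gap, because none of these steps asks about surgery.

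Third, Section 5.2 states no purpose for exclusion 2. It could be meant only for patients admitted for immediate surgery. That is fair: protection of the study window is an inference, drawn from the matching six hours and from Section 9.2.3, which allows only for unexpected surgery. Under either purpose, foreseen surgery in the study period is left unaddressed.

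Fourth, it would be too strong to say that the criterion excludes no one after hour 6. Read literally, it still removes someone approached at hour 10 whose surgery had been expected within six hours of admission and was then done or delayed. The point holds for surgery foreseen for after hour 6.

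**Conclusion.** The mismatch is in the current text and the arithmetic follows from it. The criterion covers max(0, 6 − t) of the six study hours, and none for entry at hour 6 or later. Followed literally, the eligibility rules admit subjects already expected to be non-evaluable.

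The size in subjects is unknown and could be zero. The 75% is a share of permitted entry hours. It would be wrong to read it as a share of subjects or of risk, since the documents give neither entry times nor how often surgery is planned in this population. The 50%, 25% and 12.5% coverage figures rest on assumed uniform entry.

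Two further readings go beyond the documents. One is that the allowance of 6 of 20 (6/20 = 30%) already counts these subjects; Section 9.2.3 speaks of unexpected surgery only. The other is that the device comparison is biased; nothing in the documents shows that, and it is not claimed.

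The conclusion assumes that the evaluable definition in Section 9.2 is applied as written, with the full six hours and three hours on each device. What remains is an avoidable number of non-evaluable enrolments. Severity: minor.

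**What to change.** Reconcile exclusion 2 in Section 5.2 with the 24-hour entry window (Sections 1.2 and 5.3) and the six-hour participation period (Section 5.4). Re-anchored to the study, it would refer to surgery anticipated between enrolment and the end of the six-hour intervention period. It would then cover all six study hours at any entry time and would match the allowance in Section 9.2.3, which is limited to unexpected surgery.

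The change is one phrase in Section 5.2. It adds no procedure, since the record is already reviewed and the clinical team already consulted before enrolment. The cost is a few more screen failures, among subjects who were not expected to become evaluable.
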